## 1. INTRODUCTION

### 1.1 Phase:

This is a phase II, single center, randomized, double-blind, placebo-controlled study assessing the effects of dexamethasone versus placebo on radiation fatigue, quality of life (QoL), and treatment interruption in patients receiving definitive treatment for head and neck and non-small cell lung cancers. Subjects will be stratified by treatment (radiation alone vs. radiation plus systemic therapy) and randomized within strata to one of two treatment arms with equal probability.

### 1.2 Indication:

Dexamethasone for the treatment of radiation related fatigue, QoL, and treatment interruption in patients receiving radiation therapy (RT) for head and neck (HN) and non-small cell lung cancer

### 1.3 Endpoints:

#### Primary

- Fatigue score assessed via the Functional Assessment of Chronic Illness-Fatigue (FACIT-F) 13-item fatigue subscale

#### Secondary

- QoL score assessed via the FACIT-F 40-item total score (27+13)
- Total days and cause of treatment interruption

### 1.4 Patient population:

Eligible subjects must be able to understand and sign the study specific subject consent form. They must be  $\geq 18$  years of age, have a KPS of  $\geq 60$  with confirmed histologic or cytologic diagnosis of HN cancer (stage I-IV) or non-small cell lung cancer (stage II & III) for which they are receiving definitive treatment with either RT alone or in combination with systemic therapy. Subjects may not be diabetic and must have recent labs as defined in the inclusion and exclusion criteria found in Section 6.

## 2. STUDY DESIGN

2.1 Phase: This is a phase II, single center, randomized, double-blind, placebo-controlled study.

2.2 Number of centers: One

This study will be performed by The University of Arizona Medical Center (UAMC) Radiation Oncology Department at both the University Campus Hospital and Orange Grove Clinic.

2.3 Number of subjects: Approximately 80

2.4 Subject participation time period:

Subjects will be enrolled in the study for approximately four months, including screening time, treatment time, and follow-up at 30 and 60 days post radiation therapy.

Subjects enrolled in this study are undergoing treatment at UAMC Main Campus or Orange Grove Clinic as part of standard of care for the treatment of HN or non-small cell lung cancer. Study subjects will be treated with either dexamethasone or placebo for 14 consecutive days during RT. Typical RT schedule is six to seven weeks in length with treatments administered Monday through Friday. Subjects will begin the taking the investigational product (dexamethasone or placebo) on RT day 16. Fatigue and QoL will be measured with validated FACIT-F patient surveys that will be completed during RT visits and 30 and 60day post RT follow-up evaluation. The number of days and cause of RT treatment interruption will also be tracked.

### SCHEMA

REGISTER	Head and Neck Cancer (Group 1)	STRATIFY	Radiation Alone (Group 1a) and (Group 2a)	STRATIFY	RANDOMIZE	ARM 1 Placebo BID
	Non-small Cell Lung Cancer (Group 2)		Radiation plus Systemic Therapy (Group 1b and Group 2b)			ARM 2 dexamethasone 4 mg BID

### 3. OBJECTIVES

- 3.1 Primary:  
To compare the effects of dexamethasone and placebo on radiation fatigue using validated measures
- 3.2 Secondary:  
To determine the effect of dexamethasone on QoL and RT treatment interruption

## 4. BACKGROUND and RATIONALE

### 4.1 Disease

Among symptoms experienced by cancer patients, fatigue has been reported as being the most common and distressing. Cancer related fatigue (CRF) is multi-factorial with comorbidities, tumor burden and treatment (i.e. surgery, chemotherapy, radiotherapy) all contributing. Survey studies have shown CRF to impact activities of daily living and quality of life (QoL) greater than pain, nausea, depression, and/or sexual dysfunction. One may postulate that both cancer and treatment related fatigue may influence a patient's ability to successfully complete therapy uninterrupted, potentially impacting disease outcomes. It has been clearly demonstrated that interruption and/or delay in completion of radiotherapy (RT) in Head and Neck (HN) and lung cancer is a strong negative predictor for loco-regional control (LRC) and overall survival (OS).

The relationship between RT and fatigue has been well described. Patients undergoing treatment for brain, HN, breast, lung, pelvis and lymphatic system cancers are best documented. In a study by Hickok et al., 372 patients receiving RT for various cancers were followed prospectively and given weekly symptom inventory surveys for a minimum of five weeks to assess fatigue. Of 160 patients who reported no fatigue at baseline, 70% were found to experience fatigue related symptoms at some point during treatment. In contrast, only 13% of patients remained fatigue free. In another study looking specifically at 117 patients receiving RT for HN cancer, Jereczek-Fossa et al. showed that all patients experienced some level of fatigue during RT with peak levels occurring at week six of treatment (see Figure 1 below).

[figure not shown]

Fig. 1. Fatigue evolution during radiotherapy (RT) for head and neck tumor. Fatigue scores assessed before, during, and after RT with use of the Multidimensional Fatigue Inventory (MFI-20) questionnaire are shown. Data are mean  $\pm$  standard deviation.

The use of corticosteroids for treatment of CRF has largely been anecdotal. Corticosteroids not only improve fatigue but also pain, nausea, and anorexia, making this an attractive option in cancer management. A prospective randomized clinical trial conducted by Moertel et al., studied the impact of dexamethasone on performance

status (PS) in patients with unresectable gastrointestinal adenocarcinoma who were deemed unsuitable for chemotherapy. Patients were randomized to receive placebo, dexamethasone 0.75 mg four times a day, or dexamethasone 1.5 mg four times a day until death or intolerability of the medication. Both choice of corticosteroid and dose were based on clinical experience at the time of study design. A total of 116 patients were included and no difference in PS or OS was detected. Some weaknesses of this study include the absence of a validated tool for measuring patient PS and low dose of corticosteroid.

Additional prospective studies for pharmacologic intervention in the management of CRF are highlighted in a 2013 review article by de Raaf and van der Rijt, where 10 trials investigating 7 medications (paroxetine, donepezil, adenosine triphosphate, L-carnitine, methylphenidate, dexamphetamine, and dexamethasone) were included. Among these studies, a significant improvement in CRF was present only in studies utilizing methylphenidate (1 of 4 studies) and dexamethasone (1 of 1 study). Corticosteroids have the potential benefit over psycho-stimulants for patients receiving RT through their anti-inflammatory properties which likely reduce treatment related edema and potential late fibrotic related complications.

A double blind, randomized, placebo-controlled trial by Yennurajalingam et al., assessed the efficacy of dexamethasone in the management of CRF. Eighty four patients were randomized to placebo or dexamethasone 4 mg twice daily for 14 days. The previously validated Functional Assessment of Chronic Illness Therapy-Fatigue (FACIT-F) was used to measure change in mean fatigue from baseline to day 15. Patients were included if they had advanced cancer, Edmonton Symptom Assessment Scale (ESAS) score  $\geq 4$ , and  $\geq 3$  of the following symptoms within 24 hours prior to enrollment: pain, fatigue, chronic nausea, anorexia/cachexia, sleep disturbances, and/or depression. Patients receiving RT were included in this study, although exact numbers were not reported. Results showed that dexamethasone significantly improved both FACIT-F subscale scores (9.0 vs. 3.1,  $P=0.008$ ) and FACIT-F total quality of life scores (18.16 vs. 7.87,  $P=0.030$ ) when compared to placebo. Adverse events were assessed with the National Cancer Institute Common Toxicity Criteria, and no significant differences were found.

Few high quality prospective randomized clinical trials have been conducted for corticosteroid use in the management of CRF. Of studies published thus far, all were non-selective for disease sites and cancer directed therapy offered, and most included patients deemed incurable and in the palliative setting. Nearly all patients undergoing chemoradiation for the definitive management of HN and lung cancers experience cancer and treatment related fatigue toward the end of their therapy, which often leads to unplanned treatment interruptions and potentially worse outcomes. We hypothesize that a short course steroid intervention midway through RT will impact fatigue related measures, QoL, treatment interruption, and potentially disease related outcomes.

#### 4.2 Investigational Product: Decadron (dexamethasone)

Corticosteroids are structurally similar to endogenous cortisol and act on target cells by regulating the transcription of target genes. Arguably their most clinically relevant side

effects involve the endocrine system, in particular adrenal suppression and hyperglycemia.

Adrenal suppression occurs in a dose and duration dependent manner, and may cause an inadequate stress response if major illness concurrently occurs. Patients receiving any corticosteroid dose for less than three weeks duration are considered unlikely to develop suppression and may stop treatment without a taper. This study will attempt to treat radiation fatigue with a 14 day non-tapered course of dexamethasone as previously published.

Hyperglycemia with corticosteroids occurs because of decreased insulin sensitivity, increased gluconeogenesis, and inhibition of insulin secretion. A typical 10-20% increase in blood glucose has been reported with up to one fifth developing steroid diabetes. No official recommendation exists on monitoring blood glucose during acute treatment. The only available guide is in the setting of chronic post-transplant therapy, which recommends screening fasting plasma glucose (FPG) levels once a week during the first four weeks.

Some have argued that FPG levels may actually be a poor marker during corticosteroid treatment because these drugs influence post-prandial levels most significantly and often do not affect fasting levels. Trence recommends checking weekly random plasma glucose (RPG) levels during corticosteroid treatment with a goal below 180 mg/dL. Similarly, Lansang and Hustak endorse RPG with a level of  $\geq 200$  and classic symptoms of diabetes for detecting glucocorticoid-induced diabetes. This cutoff is taken directly from diabetes guidelines and is an official criterion for the diagnosis of diabetes.

As an added safety measure this study will monitor RPG levels during dexamethasone treatment since they are influenced more than FPG and we wish to avoid fasting in our patient population. Encouraging fasting in patients who commonly experience anorexia and weight loss from both disease and RT would promote suboptimal care.

#### 4.3 Pre-clinical Experience

A 1988 review article by Ettinger and Portenoy highlighted the utilization of corticosteroids in cancer symptom management. Use was described as widely accepted in practice despite a lack of well-controlled studies. Dose selection has been derived empirically from pain dosages and the regimen of dexamethasone 4 mg every 6 hours has been suggested. More recently, a 2009 National Comprehensive Cancer Network survey of 1,000 oncologists reported that 23% to 33% frequently prescribe corticosteroids for CRF at the end of life.

#### 4.4 Clinical Experience

Preliminary clinical data from one prior phase II study performed at MD Anderson support that dexamethasone 4 mg by mouth twice daily is more effective than placebo in improving CRF and QoL in patients with advanced cancer. No significant difference in adverse effects was observed between groups.

## **5. INVESTIGATIONAL PRODUCT**

### **5.1 Investigational Product (IP)**

Dexamethasone 4 mg taken orally twice daily for 14 days or placebo taken orally twice daily for 14 days

### **5.2 Investigational Product Supply**

The IP is an FDA approved drug which will be supplied from the UMC investigational pharmacy. The dexamethasone will either be cut in half or crushed and placed in a capsule. A placebo that is made from Equal sugar substitute will be placed in the same type of capsule as the dexamethasone and only the pharmacist will know if the medication given to the patient is dexamethasone or placebo.

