## **7. STUDY PLAN**

### **7.1 Treatment Regimen**

Subjects will be stratified by type of disease and whether or not they will be receiving chemotherapy and then randomly assigned to receive either dexamethasone 4 mg twice daily or placebo twice daily for 14 days via the oral route. Assignment of IP will be done in a double-blinded fashion. Both active drug and placebo will be compounded to look identical in appearance. Treatment with IP will start on day 16 of RT and subjects will complete a pill diary in order to track their medication adherence. Subjects will be advised to take the IP with food at approximately 8 a.m. and 2 p.m.  $\pm 2$  hours. Subjects will also be advised that if they are experiencing difficulty swallowing as a result of treatment and are unable to swallow a pill, they can mix the contents of the capsule with either applesauce or any liquid. They will also be asked to complete an observation form, beginning with their first day of IP and continuing until 60 days post RT, describing any side effects or problems they experience while on the study medication.

Subject's RPG levels will be monitored prior to starting IP via glucometer on RT days 15 [ $\pm 2$  days], 20 [ $\pm 2$  days] and 25 [ $\pm 2$  days], with optional testing per physician discretion on the final day of RT and 30 and 60 day RT follow-up visits. If subjects have had blood drawn within the  $\pm 2$  day window that includes glucose testing, they will not be required to have a fingerstick blood glucose test. Subjects who meet a modified Common Terminology Criteria Version 4.0 for adverse events Grade 3 hyperglycemia criteria, RPG level greater than or equal

to 250 mg/dL, will be told to discontinue IP immediately and have a repeat RPG level performed in 3 RT days.

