Subjects will be seen once per week per standard of care for on-treatment visits. Weight, BP and evaluation of side effects (including mucositis evaluation) will be performed. FACIT-F 13-item fatigue subscale and FACIT-F 27-item total questionnaires will be completed by subjects during screening and on RT days 5 [ $\pm 2$  days], 10 [ $\pm 2$  days], 15 (day prior to IP start) [ $\pm 2$  days], 20 [ $\pm 2$  days], 25 [ $\pm 2$  days], 26 [ $\pm 2$  days] and 30 (or last day of RT if course extended) [ $\pm 2$  days] along with 30 day post RT follow-up [ $\pm 7$  days] and 60 day post RT follow-up [ $\pm 7$  days] to assess fatigue and QoL. If a subject discontinues IP early for any reason they will still complete FACIT surveys on RT day 26 [ $\pm 2$  days] so they can be included in an intention to treat analysis. Furthermore, if a patient has their RT extended, they will complete FACIT surveys on their last RT day rather than RT day 30.

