### 8.3 Investigational Product Dose Delay

Subjects will start taking IP on RT day 16. The IP will be taken twice per day continuously for 14 days. If there are RT interruptions prior to the IP start date, subjects will still begin IP treatment on RT day 16. If RT interruptions occur while taking the IP, subjects should continue IP per protocol. All subjects will take a full 14 day continuous course of IP unless instructed by the principal investigator to discontinue because of elevated RPG or unacceptable toxicity as deemed appropriate by the Principal Investigator. Subjects will be advised to take the IP with food at 8 a.m. and 2 p.m  $\pm 2$  hours. Subjects unable to swallow the IP capsule whole may open the capsule and sprinkle the contents into applesauce for assistance with administration.

If a subject misses a scheduled dose of IP within the recommended window, they should skip the missed dose and resume treatment at the next scheduled time. They should never double-up doses. Treatment course will not be extended beyond 14 days to compensate for missed doses. Subjects will stop treatment after 14 total days have passed and return any missed doses or unused drug as described in Section 5.

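### Placebo capsules contain sweetener and active capsules contain cut or crushed dexamethasone, yet patients who cannot swallow them may take the contents, which could reveal the arm while they self-report the primary outcome

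*Combined protocol and SAP*

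**What the plan says.** Section 5.2 describes the two products. For the active arm: "The dexamethasone will either be cut in half or crushed and placed in a capsule". For the control arm: "A placebo that is made from Equal sugar substitute will be placed in the same type of capsule as the dexamethasone". No common excipient is named; the shared feature is the type of capsule.

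Section 7.1 gives the matching requirement: "Both active drug and placebo will be compounded to look identical in appearance". It does not mention taste and does not say whether it covers the contents or only the closed capsule.

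Section 7.1 foresees that radiotherapy may leave some patients without the ability to get the capsule down, and its advice to them is that "they can mix the contents of the capsule with either applesauce or any liquid". Section 8.3 says that such patients "may open the capsule and sprinkle the contents into applesauce for assistance with administration", and names applesauce only.

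The primary outcome (Section 16) is the change in the FACIT-F 13-item fatigue subscale from RT day 15 to RT day 26. It is scored by the patient; Section 7.1 says of the FACIT-F that "questionnaires will be completed by subjects during screening" and at set RT days and follow-up visits. Study drug starts on RT day 16.

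**The concern.** The blind rests on the capsule shell, and the protocol allows the shell to be removed. Once it is open, one arm is taking a sugar substitute and the other a corticosteroid tablet in pieces or powder. A patient may be able to taste the difference, or see it if the tablet was only cut.

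Opening is foreseeable. The population includes head and neck cancer patients on definitive radiotherapy, Section 7.1 anticipates swallowing difficulty caused by treatment, and at weekly visits "evaluation of side effects (including mucositis evaluation) will be performed". Dosing falls in the middle and later part of the course.

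The outcome is exposed because the patient is the assessor. A placebo patient who recognises the sweetener may report less improvement, which favours dexamethasone. A dexamethasone patient who tastes sweet applesauce and concludes it is placebo would move the result towards no difference. The exclusions in Section 6.2 for sensitivity to Equal, allergy to sugar substitute and phenylketonuria could hint at what the placebo is, although the consent text is not available to check this. The documents describe no assessment of the blind and no record of who opened capsules.

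There is also a conflict of wording: a tablet cut in half does not fit instructions to sprinkle or mix the contents, which imply a powder.

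**Working it through.** **Inputs from Section 16.** Mean improvement 9.0 (SD 10.30) on dexamethasone and 3.1 (SD 9.59) on placebo; one-sided alpha 0.05; 36 evaluable patients per group for 80% power; 40 enrolled per group to allow 10% drop-out.

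**Reproducing the plan's figure (normal approximation).**
- Difference = 9.0 − 3.1 = 5.9.
- SD = √((10.30² + 9.59²)/2) = 9.951.
- SE at 36 per group = 9.951 × √(2/36) = 2.346.
- Power = Φ(5.9/2.346 − 1.645) = 80.8% (80.1% by the noncentral t).
- 36/(1 − 0.10) = 40.

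The stated sample size reproduces and is not in dispute.

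**Size of a possible bias.** Every input here is an assumption:

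bias = share opening × share guessing placebo × points lost

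Guessing is taken as 25% to 100% of openers, and points lost as 1 to 3.1. The upper value removes the whole placebo improvement assumed in Section 16.

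- If only placebo patients guess: type I error = 1 − Φ(1.645 − bias/2.346).
- If only dexamethasone patients guess placebo: power = Φ((5.9 − bias)/2.346 − 1.645).

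| Opening | Openers per arm | Bias (points) | Type I error | Power |
|---|---|---|---|---|
| 10%, low | 3.6 | 0.10 × 0.25 × 1 = 0.025 | 5.1% | 80.5% |
| 10%, high | 3.6 | 0.10 × 1 × 3.1 = 0.31 | 6.5% | 77.0% |
| 30%, low | 10.8 | 0.30 × 0.25 × 1 = 0.075 | 5.3% | 79.9% |
| 30%, high | 10.8 | 0.30 × 1 × 3.1 = 0.93 | 10.6% | 68.2% |

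The last two columns are alternatives, not joint effects. If equal shares guess placebo in both arms, with equal loss, the net bias is zero.

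**What it takes to double the error.** A type I error of 10% needs a bias of (1.645 − 1.282) × 2.346 = 0.85 points. At 3.1 points each, 0.85/3.1 = 27% of the placebo arm would have to open the capsule, recognise the sweetener and lose the full amount.

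**Wider assumptions.** If the shift in the between-arm difference among openers were 2 points at 10% opening (bias 0.2), the type I error would be 5.9%. At 25% opening and 4 points (bias 1.0) it would be 11.2%. At 50% and 6 points (bias 3.0) it would be 35.7%, but that supposes a shift larger than the planned effect of 5.9 in half the patients.

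**Could it be sorted out afterwards?** A comparison of arms among openers alone would have SE 9.951 × √(2/4) = 7.0 points with 4 per arm, or 9.951 × √(2/11) = 4.2 with 11 per arm. The 95% half-widths are at least 13.8 and 8.3 points, both wider than 5.9. Opening also happens after randomization, so the comparison would not be protected by it.

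**The case against.** The strongest reply is that the key fact is not documented. Unblinding needs a chain: the patient cannot swallow, opens the capsule, detects a difference through applesauce or liquid, reads it as placebo, and scores differently. The documents support the first two steps as possible and give no frequency for any of them. They do not describe the taste of either product. Even the direction is unsettled, since wrong guesses in the dexamethasone arm pull the other way.

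Second, the appearance requirement in Section 7.1 refers to the drug and the placebo, not expressly to the closed capsule. If it covers the contents, a visible half tablet would already breach it. Third, the pharmacy forms listed at 30.6 and 30.7 are not reproduced and may specify a filler. Fourth, the inclusion criteria require patients to be able to tolerate oral medication.

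Much of this stands as a limit on size and certainty. It does not remove the problem. The appearance requirement leaves taste untouched and, if it does cover the contents, is hard to reconcile with the cut-tablet option in Section 5.2. The oral-medication criterion applies at entry and does not prevent later difficulty swallowing. If the pharmacy forms already match the contents, one sentence in Section 5.2 settles the matter.

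**Conclusion.** The concern holds. Followed as written, the plan leaves a foreseeable route to unblinding for patients who take the capsule contents, in a trial whose primary outcome those patients report themselves.

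The size is unknown and probably modest. At 10% opening the effect is minor under the main assumptions; it becomes material only if opening and recognition are both common. The 3.1-point placebo gain used as the upper loss comes from advanced-cancer patients. Section 4.1 cites fatigue peaking at week six of radiotherapy, so a gain of that size may not occur here. The direction depends on which arm does the guessing.

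This is a change that should be made rather than a fatal flaw: the loss cannot be undone in the analysis, and prevention before dispensing is inexpensive. Confidence is medium, because the taste difference is inferred and the pharmacy forms and consent text were not available.

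**What to change.** - **Section 5.2:** remove the option of cutting the tablet in half. Require the active contents to be fully powdered and blended with the same Equal excipient as the placebo, to a matched fill, with the dexamethasone amount per capsule unchanged. If forms 30.6 and 30.7 already require this, say so here.
- **Section 7.1:** extend the matching requirement to the capsule contents, covering look and, as far as practicable, taste.
- **Sections 7.1 and 8.3:** reconcile the two descriptions of how the contents may be taken.
- **Pill diary (30.5):** add a yes/no item for whether the capsule was opened, if there is none, and report openers per arm descriptively. Do not analyse the primary outcome by opening, for the reasons shown in the working.

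The cost is a compounding instruction, small wording changes and at most one diary item, with no extra patients, visits or tests. The drawbacks are slightly more compounding work and sweetener given to the active arm, for which Section 6.2 already screens everyone. Tablet strength and capsule size are not stated, so the pharmacy must confirm that the blend fits. Blending reduces a taste difference but does not guarantee its removal.
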